10.1.2.8 Visit 8: Week 39 (±3 days)

Before dosing, the following assessments will be performed as listed in the study flow chart, [Section 1.3.2](#), which should be done in the following order:

- Whenever possible, the following scales and questionnaires should be done prior to clinical interaction with the Investigator:
 - BDI-II ([Appendix L](#))
 - PGIC ([Appendix N](#))
 - PDQ-39 ([Appendix O](#))
 - EQ-5D ([Appendix P](#))
 - HRPQ ([Appendix R](#))
 - FES ([Appendix Q](#))
- MDS-UPDRS, including H&Y ([Appendix F](#))
- PD-CRS ([Appendix G](#))
- Other questionnaires and scales
 - MoCA ([Appendix I](#))

- Oral SDMT ([Appendix J](#))
- TMT-A; TMT-B ([Appendix K](#))
- Review of concomitant medications
- General neurological examination
- Visual acuity check, slit lamp examination, and fundoscopy without pupil dilation
- Vital signs: systolic and diastolic blood pressure (mm Hg), heart rate (bpm), respiratory rate (breaths/minute), and temperature (°C)
- Laboratory assessments (to be performed by the central laboratory):
 - Hematology: CBC, with differential and platelet count; coagulation profile: PT, PTT, and INR
 - Biochemistry: Sodium, potassium, chloride, calcium, ALT, AST, GGT, ALP, total and conjugated bilirubin, urea, serum creatinine, glucose, albumin, total proteins
- Urinalysis (dipstick) including glucose, protein, bilirubin, urobilinogen, pH, specific gravity, blood, ketones, nitrite, and leucocytes. Central urinalysis will be performed if any abnormality is observed in the urinalysis dipstick test.
- Urine pregnancy test (for WOCBP)
- Review of current medical conditions, with AE/SAE reporting (if any)
- Blood sampling for biomarker analysis
- Dispense IMP

Remind patient to return to the clinic for next visit, bring their diary and any remaining capsules.

Remind patient to not take the dose at home on the clinic visiting day, the IMP will be taken at clinic.

10.1.2.9 Visit 9: Week 52 (±14 days)

Visit 9 will be the last study visit of the blinded treatment period in Part 2.

Before dosing, the following assessments will be performed as listed in the study flow chart, [Section 1.3.2](#), which must be done in the following order:

- Whenever possible, the following scales and questionnaires should be done prior to clinical interaction with the Investigator:
 - BDI-II ([Appendix L](#))
 - PGIC ([Appendix N](#))
 - CGI ([Appendix M](#))
 - PDQ-39 ([Appendix O](#))
 - EQ-5D ([Appendix P](#))

- HRPQ ([Appendix R](#))
- FES ([Appendix Q](#))
- MDS-UPDRS, including H&Y ([Appendix F](#))
- PD-CRS ([Appendix G](#))
- Other questionnaires and scales
 - MoCA ([Appendix I](#))
 - Oral SDMT ([Appendix J](#))
 - TMT-A; TMT-B ([Appendix K](#))
- Review concomitant medications
- Physical examination
- General neurological examination
- Record of body weight measurement
- Vital signs (orthostatic): systolic and diastolic blood pressure (mm Hg), heart rate (bpm), respiratory rate (breaths/minute), and temperature (°C)
- 12-lead ECG
- Laboratory assessments (to be performed by the central laboratory):
 - Hematology: CBC, with differential and platelet count; coagulation profile: PT, PTT, and INR
 - Biochemistry: Sodium, potassium, chloride, calcium, ALT, AST, GGT, ALP, total and conjugated bilirubin, urea, serum creatinine, glucose, albumin, total proteins
- Urinalysis (dipstick) including glucose, protein, bilirubin, urobilinogen, pH, specific gravity, blood, ketones, nitrite, and leucocytes. Central urinalysis will be performed if any abnormality is observed in the urinalysis dipstick test.
- Urine pregnancy test (for WOCBP)
- Review of current medical conditions, with AE/SAE reporting (if any)
- Blood sampling for biomarker analyses, GCase activity and PK (as listed in study flow chart [Section 1.4.2](#))
- Pharmacogenetics DNA sample (optional; not applicable in Israel [[Appendix T](#)])
- Evaluate patients for eligibility (inclusion/exclusion criteria as listed in [Section 7.1](#), [Section 7.2](#), and [Section 10.1.2.10](#)) to transition to LTFU and receive GZ/SAR402671 treatment
- Full ophthalmology examination and photography (must be performed after the neurological examination)
- DAT scan

- Lumbar puncture for collection of CSF for PK (as listed in study flow chart [Section 1.4.2](#)) and biomarker analyses
- Dispense IMP (the results for all Week 52 assessments, required to check inclusion/exclusion criteria, must be received and reviewed before the Week 52 visit is registered in IVRS for Week 52 IMP dispensation)

Remind patient to return to the clinic for next visit, bring their diary and any remaining capsules, if patient is enrolled in the LTFU period.

Remind patient to not take the dose at home on the clinic visiting day, the IMP will be taken at clinic.

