	
 • Week 26: 
 - C_{through} - Concentration at any time within 2 to 4 hours after administration of GZ/SAR402671 on visit day. • Week 52: 
 - C_{through} - Concentration at any time within 2 to 4 hours after administration of GZ/SAR402671 on visit day. 
Cerebrospinal fluid parameters include:
 
 • Day -14 to Day 1: pre-dose concentration • Week 52 (all patients): concentration at any time within 2 to 4 hours after administration of GZ/SAR402671 on visit days. 
NOTE: Plasma and CSF collections for the same time points at Week 52 should be performed in as close succession as possible.
 
Exploratory GZ/SAR402671 metabolite PK profiling and/or metabolite exposure analysis may be performed on plasma and CSF samples collected during Part 1 and Part 2 of the study.
 
Safety endpoints
 
 • Incidence, relationship to study drug and resolution of treatment-emergent adverse events (TEAEs), SAE, TEAE/SAE leading to study drug or study discontinuation. • Ophthalmological assessments. Visual acuity and lens evaluation will be performed according to the Lens Opacity Classification System II (LOCSII) for monitoring potential cataract development.

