- n DNA sample will be stored to support possible future investigation of potential biomarkers for response to GZ/SAR402671. The patient must sign a separate and optional consent form for pharmacogenetics (DNA) analysis only. Of note, the first DNA sample should be collected at baseline after eligibility criteria are met, but it may be collected at any visit during the study. This sample will not be required for patients from Part 1 to enroll in Part 2. The second DNA sample should be collected at Week 52 or at any visit after Week 52.
- o Multiple plasma PK assessments occur on this study day. See detailed flowcharts in [Section 1.4.2](#) for timing of assessments.
- p Cerebrospinal fluid PK assessments. See detailed flowcharts in [Section 1.4.2](#) for more detail with respect to the timing of assessments.
- q Baseline efficacy assessments should be conducted **prior to GZ/SAR402671 administration on Day 1**. For patients already on PD medications at the time of randomization, all efficacy assessments must be done in the patient's "OFF" state (no PD medication may be taken for at least 12 hours prior to the first efficacy assessment). See also footnote s.
- r Baseline DAT scan may be done within 7 days prior to randomization (Day -7 to Day -1) or on the day of randomization (Day 1 pre-dose).
- s Baseline H&Y for patients on a stable dose of PD medication must be done on the "ON" state (see inclusion criterion [I 05](#)).
- t At screening, patients with BDI-II of 20-28, inclusive, should be evaluated by a mental health specialist before the Investigator can determine if the patient would be able to fully participate in the trial. Patients with a BDI-II of >28 (severe depression) at screening will be excluded.
- u Visit window extended up to 3 months, during Covid-19 outbreak ([Section 10.1.2](#)).

Note: When several items take place at the same time, the following order should be respected: vital signs; plasma sampling for pharmacodynamics, PK, and safety; LP, IMP administration.

Note: Pregnancy testing after screening will be by urine dipstick testing and **must** be conducted prior to imaging; pregnancy testing is required for all female patients capable of bearing children. Pregnancy tests may be performed more frequently in some countries due to local legislations related to WOCBP randomized in clinical trials.

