1.4.2 Part 2: Treatment phase

	Week 0/day 1						Week 0/ day 2		Week 2 (±3 days)		Week 26 (±3 days)			Week 52 (±14 days)		
Time (hour)	Pre-dose	0 h	1 h ^a	2 h ^b	4 h ^c	8 h ^d	24 h ^e	0 h	Pre-dose	0 h	Pre-dose	0 h	2 ^b - 4 ^c h	Pre-dose	0 h	2 ^b - 4 ^c h
GZ/SAR402671 or placebo		X						X (NO DRUG HOLIDAY)		X		X			X	
Plasma sample for PK	P01 ^f		P02	P03	P04	P05	P06 ^f		P07 ^f		P08 ^f		P09 ^g	P10 ^f		P11 ^g
CSF sample for PK	C01 ^h															C02 ^g

Abbreviations: CSF: cerebrospinal fluid; LP: lumbar puncture; PK: pharmacokinetics.

a Blood sample must be collected within 1 hour ±10 minutes.

b Blood sample must be collected within 2 hours ±15 minutes.

c Blood sample must be collected within 4 hours ±30 minutes.

d Blood sample must be collected within 8 hours ±60 minutes.

e Blood sample must be collected within 24 hours ±60 minutes after the Day 1 dose.

f Sample must be collected within 1 hour before oral administration of GZ/SAR402671. On these days, patients will take GZ/SAR402671 at the clinical site.

g Sample to be collected within 2 to 4 hours post GZ/SAR402671 administration (plasma and CSF samples in the same patient should be collected as close as possible).

h The LP may be done during the screening period within 14 days prior to randomization (Day -14 to Day -1) or on the day of randomization (Day 1, pre-dose). The CSF sample for PK will be done at the same time. LP at baseline will not be required to confirm eligibility of patients from Part 1 to enroll in Part 2.

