9.4.2 Pharmacokinetics

9.4.2.1 Sampling time

The sampling times for blood and CSF collection in Part 1 and Part 2 can be found in the study flow charts (Section 1.4) and in a separate laboratory manual.

Plasma and CSF collections for the same time points at Week 4 in Part 1 and at Week 52 in Part 2 should be performed in as close succession as possible.

Plasma parameters in Part 1 will include:

- Day 1 (single dose administration): maximum plasma concentration observed (C_{max}), t_{max} , and area under the plasma concentration versus time curve calculated using the trapezoidal method over a predefined time period (from time $t=0$ to 24 hours [AUC_{0-24}], and from $t=0$ to 48 hours [AUC_{0-48}])
- Week 2: plasma concentration observed just before treatment administration during repeated dosing (C_{trough})
- Week 4: C_{trough} , C_{max} , t_{max} , AUC_{0-24} , and apparent total body clearance of a drug at steady state after oral administration (CL_{ss}/F ; calculated using the following equation: $CL_{ss}/F = \text{Dose}/AUC_{\tau}$, where τ is the dosing interval)
- Week 8: C_{trough}

Cerebrospinal fluid parameters in Part 1 will include:

- Day -14 to Day 1: pre-dose concentration
- Week 4: Concentration at any time within 2 to 4 hours after administration of GZ/SAR402671

Plasma parameters in Part 2 will include:

- Day 1 (single dose administration): C_{max} , t_{max} , AUC_{0-24}
- Week 2: C_{trough}
- Week 26:
 - C_{trough}
 - Concentration at any time within 2 to 4 hours after administration of GZ/SAR402671 on visit day.
- Week 52:
 - C_{trough}
 - Concentration at any time within 2 to 4 hours after administration of GZ/SAR402671 on visit day.

Cerebrospinal fluid parameters in Part 2 will include:

- Day -14 to Day 1: pre-dose concentration
- Week 52 (all patients): Concentration at any time within 2 to 4 hours after administration of GZ/SAR402671 on visit day.

The number of samples per patient is shown in [Table 2](#).

Table 2 - Number of samples for pharmacokinetics assessment

Type of Samples	Plasma			Cerebrospinal Fluid		
	15 non-Japanese patients in Part 1	12 Japanese patients in Part 1	216 patients in Part 2	15 non-Japanese patients in Part 1	12 Japanese patients in Part 1	216 patients in Part 2
Total number of sample timepoints by patient ^a	15	15	11	2	2	2
Total number of samples for study ^a	225	180	2376	30	24	432

^a Approximate total number of samples.

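### Section 10.1.2.9 puts the Week 52 lumbar puncture and all PK blood before dosing, but the PK chart and the CSF measure time the CSF sample and plasma P11 at 2 to 4 hours after the dose

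*Protocol*

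**What the plan says.** **Visit text.** Protocol Section 10.1.2.9 introduces the Week 52 list with "Before dosing, the following assessments will be performed as listed in the study flow chart" and adds "which must be done in the following order". One item covers blood for biomarkers, GCase activity and PK. A later item reads "Lumbar puncture for collection of CSF for PK (as listed in study flow chart" and cites Section 1.4.2; the same puncture supplies the CSF biomarkers. The list includes dispensing of study drug but no step for taking the day's dose, although the section closes by saying that this dose is taken at the clinic.

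**PK chart.** Section 1.4.2 puts the Week 52 dose at 0 h, plasma P10 before it, and plasma P11 and CSF C02 after it. Footnote g, which applies to P11 and C02, says "Sample to be collected within 2 to 4 hours post GZ/SAR402671 administration".

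**Measure definition.** The synopsis gives the CSF parameter as "Week 52 (all patients): concentration at any time within 2 to 4 hours after administration of GZ/SAR402671 on visit days". Section 9.4.2.1 repeats it: "Week 52 (all patients): Concentration at any time within 2 to 4 hours after administration of GZ/SAR402671 on visit day". It adds that plasma and CSF collection for the same time point "at Week 52 in Part 2 should be performed in as close succession as possible".

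**The concern.** The visit text and the PK chart give opposite positions, relative to the dose, for the same two samples. Sites work through a visit from its list, and at Week 52 the list's order is mandatory. Amendment 04 changed should to must for this visit and for Day 1. Of the Part 2 visits with the pre-dose heading, only Week 52 has a lumbar puncture.

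Week 52 is the only on-treatment CSF collection in Part 2, so a mistimed sample cannot be replaced by one from another visit. The result concerned is the descriptive summary of CSF exposure. CSF GL-1, which serves a secondary pharmacodynamic objective in Section 5.2.2, comes from the same puncture, so its timing may move too.

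**Working it through.** The plan states no figure to reproduce. The check compares the passages and then sizes the consequence.

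**Step 1: instructions side by side**

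| Source | Week 52 CSF (C02) | Week 52 plasma P11 |
|---|---|---|
| 10.1.2.9, heading and mandatory order | before the dose | before the dose (inside the PK blood item) |
| 10.1.2.9, cross-reference to 1.4.2 | 2 to 4 h after | 2 to 4 h after |
| 1.4.2, footnote g | 2 to 4 h after | 2 to 4 h after |
| Synopsis and 9.4.2.1 | 2 to 4 h after | 2 to 4 h after |

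The heading in the first row conflicts with every other row. Plasma P10 is a true pre-dose sample, so one bullet covers both a pre-dose and a post-dose draw.

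**Step 2: what a literal reading produces.** PK blood precedes the lumbar puncture in the list. A site that obeys the heading for every item takes both before the dose, about 24 h after the previous one. A site that follows Section 1.4.2 takes both at 2 to 4 h after the dose.

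**Step 3: size of the timing error.**

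Inputs:
- Terminal half-life 31.3 h and plasma tmax 2 to 3 h (Section 4.2.1, Phase 1).
- Once-daily dosing, so a 24 h interval (Section 8.1).
- Assumptions: steady state, one-compartment kinetics, and CSF proportional to plasma.

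Simple decline from time t after the dose to the next trough: ratio = exp(−ln 2 × (24 − t) / 31.3).
- t = 2 h: exp(−0.6931 × 22 / 31.3) = 0.614
- t = 3 h: exp(−0.6931 × 21 / 31.3) = 0.628
- t = 4 h: exp(−0.6931 × 20 / 31.3) = 0.642

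One-compartment model with first-order absorption, the absorption rate solved to give the stated tmax, trough divided by C(t):

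| tmax | t = 2 h | t = 3 h | t = 4 h |
|---|---|---|---|
| 2 h | 0.617 | 0.628 | 0.642 |
| 3 h | 0.631 | 0.632 | 0.643 |

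Across both calculations the trough is 0.61 to 0.64 of the 2 to 4 h value. A pre-dose sample would therefore be about 36 to 39% lower (1 − 0.642 = 0.358; 1 − 0.614 = 0.386).

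**The case against.** The strongest defence is that the protocol names its source for timing. Section 9.4.2.1 refers sites to the Section 1.4 charts and a laboratory manual, and the lumbar puncture line itself cites Section 1.4.2. Nor are the visit lists strict clock sequences. The Day 1 list in Section 10.1.2.2 is also mandatory in order, yet places PK blood running to 8 h after the dose ahead of the pre-dose DAT scan and lumbar puncture. The Week 26 list has the same pre-dose heading but includes P09, timed at 2 to 4 h after the dose. Sites have therefore already had to take PK times from the chart. This lowers the risk. It does not reconcile the Week 52 heading with the chart it cites, and the laboratory manual is not available to settle the matter.

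Three stronger readings are tempting, and the documents do not support them:

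- **The flow-chart note as a second contradiction.** The note in Section 1.3.2 gives the order "plasma sampling for pharmacodynamics, PK, and safety; LP, IMP administration", but only for items falling at the same time. In the PK chart the dose and C02 do not coincide. The same note stands in Part 1 beside a Week 4 lumbar puncture timed at 2 to 4 h after the dose.
- **A trough CSF sample paired with a near-peak P11.** PK blood comes before the lumbar puncture in the mandatory order, so a site that keeps that order and draws P11 at 2 to 4 h does the puncture after the dose as well. The mismatched pair requires breaking the order.
- **A biased CSF/plasma ratio or a lost comparison with Part 1.** Section 11.4.4 plans descriptive CSF summaries, with Parts 1 and 2 described separately. It names neither a ratio nor a comparison of CSF between the parts. Dose selection rests on Part 1 data, which this does not touch.

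**Conclusion.** The contradiction is real and limited in reach. The Week 52 heading and mandatory order cannot be followed together with Section 1.4.2, the synopsis and Section 9.4.2.1. A literal reading would move the only on-treatment Part 2 CSF sample, and possibly P11, to before the dose.

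The 36 to 39% figure rests on CSF tracking plasma. The protocol gives no human CSF kinetics and says in Section 4.2.1 that human CSF exposure had yet to be investigated. If CSF lags plasma, the gap could be smaller or different. How many sites would read the heading literally is unknown. Mixed practice would blur the CSF exposure summary, but would not make it uninterpretable if actual times are recorded and used.

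The point touches exploratory CSF pharmacokinetics and possibly the timing of CSF GL-1. The primary and secondary efficacy analyses are unaffected.

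**What to change.** 1. Reconcile the lead-in and order of Section 10.1.2.9 with Section 1.4.2, so that the items the PK chart times after dosing (C02 and P11) no longer stand under the pre-dose heading. Splitting the PK blood item into P10 and P11 would make this explicit. The note in Section 1.3.2 needs no change.
2. Summarise Week 52 CSF and P11 by actual recorded time after dose, and keep samples outside the 2 to 4 h window out of the 2 to 4 h summary. The statistical analysis plan is not shown and may already provide for this, so its absence from the protocol is not counted as a fault.

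The cost is a text edit in one section and a line in the PK analysis, with no added visit or procedure. The rationale for amendment 05 planned the analysis of the 52-week results for the first quarter of 2021, and amendment 06 is dated February 2021. Many Week 52 samples may therefore already have been taken, and for those the second step is the one that still helps.

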10.1.2.10 Long term follow-up period (Period 3)

Patients who complete the 52 weeks of double-blinded treatment and who continue to meet inclusion criteria [I 06](#), [I 07](#), [I 08](#), and [I 09](#) and none of the exclusion criteria (exclusion criteria [E 02](#), [E 03](#), [E 05](#), and [E 06](#) will not need to be rechecked) will be eligible to enroll to the LTFU period (Period 3) where they will continue to receive appropriate monitoring and will receive GZ/SAR402671 treatment after Visit 9. It is important to note that patients will not be informed of when the switch will occur, nor will the person(s) performing any of the evaluations.

Throughout Period 3, a visit window of ± 7 days for all visits is acceptable using Day 1 as reference.

During this period, a clinic visit will be scheduled at 6-month intervals (Weeks 78, 104, 130, 156, 182, and 208) and patients will receive GZ/SAR402671, orally, at the clinic. For Japanese patients only, additional clinic visit will be scheduled at Weeks 65, 91, 117, 143, 169, and 195 (Visits 9.1, 10.1, 11.1, 12.1, 13.1, and 14.1) in addition to the above 6-month interval visits.

Before dosing, the following assessments will be performed at each study visit (every 6 months), as listed in the study flow chart, [Section 1.3.3](#), which should be done in the following order:

- Whenever possible, the following scales and questionnaires should be done prior to clinical interaction with the Investigator:
 - BDI-II ([Appendix L](#))
 - PDQ-39 ([Appendix O](#))
 - EQ-5D ([Appendix P](#))
 - HRPQ ([Appendix R](#))
 - FES ([Appendix Q](#))
- MDS-UPDRS, including H&Y ([Appendix F](#))
- PD-CRS ([Appendix G](#))
- Other questionnaires and scales
 - MoCA ([Appendix I](#))

- Oral SDMT ([Appendix J](#))
- TMT-A; TMT-B ([Appendix K](#))
- Review of concomitant medications (every 3 months [13 weeks] for Japanese patients only)
- General neurological examination
- Visual acuity check, slit lamp examination, and fundoscopy without pupil dilation at Visits 10, 12, and 14; at Visits 11, 13, and 15, patients will have a full ophthalmology examination and photography (must be performed after the neurological examination)
- Vital signs: systolic and diastolic blood pressure (mm Hg), heart rate (bpm), respiratory rate (breaths/minute), and temperature (°C) (every 3 months [13 weeks] for Japanese patients only)
- Urine pregnancy test (for WOCBP)
- Review of current medical conditions, with AE/SAE reporting (if any) (every 3 months [13 weeks] for Japanese patients only)
- Dispense IMP

At Visit 11/Week 104, Visit 13/Week 156, and Visit 15/Week 208 (ie, yearly), the following additional assessments will be performed, as listed in the study flow chart, [Section 1.3.3](#):

- Blood sampling for biomarker analysis
- Physical examination and record of body weight measurement
- 12-lead ECG
- Laboratory assessments (to be performed by the central laboratory):
 - Hematology: CBC, with differential and platelet count; coagulation profile: PT, PTT, and INR
 - Biochemistry: Sodium, potassium, chloride, calcium, ALT, AST, GGT, ALP, total and conjugated bilirubin, urea, serum creatinine, glucose, albumin, total proteins
- Urinalysis (dipstick) including glucose, protein, bilirubin, urobilinogen, pH, specific gravity, blood, ketones, nitrite, and leucocytes. Central urinalysis will be performed if any abnormality is observed in the urinalysis dipstick test.
- DAT scan
- Dispense IMP (except Visit 15/Week 208)
- Retrieve patient diary (at Visit 15/Week 208, only for patients who will transition to a long-term study with GZ/SAR402671).

Remind patient to return to the clinic for next visit.

Remind patient to not take the dose at home on the clinic visiting day, the IMP will be taken at clinic.

At Visit 15 (Week 208), patients will receive their last dose of GZ/SAR402671 at the clinic.

Visit 15 (Week 208) will be the last study visit for patients who will transition to a long-term study with GZ/SAR402671.

10.1.2.11 Eight-week follow-up visit (Period 4, end-of-study visit, Visit 16: Week 216 ±14 days)

This will be the last study visit. Patients who prematurely and permanently discontinue study medication should complete an end of treatment assessment visit (similar to Week 52/end of treatment visit for Period 2, Part 2) followed by a 8-week post-treatment follow-up visit (Visit 16). The following assessments will be performed as listed in the study flow chart, [Section 1.3.3](#), which should be done in the following order:

- BDI-II (Appendix L)
- MDS-UPDRS, including H&Y ([Appendix F](#))
- Review of concomitant medications
- Physical examination
- General neurological examination
- Visual acuity check, slit lamp examination, and fundoscopy without pupil dilation
- Vital signs: systolic and diastolic blood pressure (mm Hg), heart rate (bpm), respiratory rate (breaths/minute), and temperature (°C)
- Review of current medical conditions, with AE/SAE reporting (if any)
- Retrieve patient diary.

